# 8.2 ADVERSE EVENTS

# 8.2.1 SEVERITY OF EVENT

**Mild** – Events require minimal or no treatment and do not interfere with the participant's daily activities.

**Moderate** – Events result in a low level of inconvenience or concern with the therapeutic measures. Moderate events may cause some interference with functioning.

**Severe** – Events interrupt a participant's usual daily activity and may require systemic drug therapy or other treatment. Severe events are usually potentially life-threatening or incapacitating.

# 8.2.2 EXPECTEDNESS

Table 4. Adverse events attributed to sildenafil in placebo-controlled randomized trials				
Adverse Event	% of patients on sildenafil reporting AE (n = 734)	% of patients on placebo reporting AE (n = 725)		
Headache	16%	4%		
Flushing	10%	1%		
Dyspepsia	7%	2%		
Nasal Congestion	4%	2%		
Urinary Tract Infection	3%	2%		

Sildenafil Treatment for Chronic Traumatic Microvascular Injuries

Abnormal vision*	3%	0%
Diarrhea	3%	1%
Dizziness	2%	1%
Rash	2%	1%

\*Abnormal Vision: Mild and transient, predominantly color tinge to vision, but increased sensitivity to light or blurred vision. In these studies, only one patient discontinued due to abnormal vision

Table 5. Adverse Events Reported by Participants in Placebo Controlled RCTs, but Equally Common in Placebo Group (occurred in <2% of participants; relationship to Viagra unknown but plausible)		
System	Adverse Event	
Body	Face swelling, light sensitivity, shock, pain, chills, accidental fall , abdominal pain, allergic reaction, chest pain, accidental injury, body or muscle weakness	
Cardiovascular	Chest pain, AV block, migraine, syncope, tachycardia, palpitation, hypotension, postural hypotension, myocardial ischemia, cerebral thrombosis, cardiac arrest, heart failure, abnormal electrocardiogram, cardiomyopathy.	
Digestive	Vomiting, glossitis, colitis, dysphagia, gastritis, gastroenteritis, esophagitis, esophagitis, stomatitis, dry mouth, liver function tests abnormal, rectal hemorrhage, gingivitis.	
Hemic and Lymphatic	Anemia and leukopenia.	
Metabolic and Nutritional	Thirst, edema, gout, unstable diabetes, hyperglycemia, peripheral edema, hyperuricemia, hypoglycemic reaction, hypernatremia.	
Musculoskeletal	Arthritis, arthrosis, myalgia, tendon rupture, tenosynovitis, bone pain, myasthenia, synovitis.	
Ataxia, hypertonia, neuralgia, neuropathy, paresthesia, tremor, vertigo,           Nervous         depression, insomnia, somnolence, abnormal dreams, reflexes decrease           hypesthesia.         hypesthesia.		
Respiratory	Asthma, dyspnea, laryngitis, pharyngitis, sinusitis, bronchitis, sputum increased, cough increased.	
Skin and Appendages	Urticaria, herpes simplex, pruritus, sweating, skin ulcer, contact dermatitis, exfoliative dermatitis.	
Special Senses	Sudden decrease or loss of hearing, mydriasis, conjunctivitis, photophobia, tinnitus, eye pain, ear pain, eye hemorrhage, cataract, dry eyes.	

Urogenital	Cystitis, nocturia, urinary frequency, breast enlargement, urinary			
orogenitar	incontinence, abnormal ejaculation, genital edema and anorgasmia.			

#### Table 6. Post-Marketing Experiences Reported in Temporal Association with the use of Viagra.

Occurred predominantly in patients who had preexisting cardiovascular risk factors. Undetermined if these events are related directly to Viagra, to sexual activity, to the patient's underlying conditions, or to a combination of these factors.

Cardiovascular and Cerebrovascular	Myocardial infarction, sudden cardiac death, ventricular arrhythmia, cerebrovascular hemorrhage, transient ischemic attack, hypertension, subarachnoid and intracerebral hemorrhages, and pulmonary hemorrhage					
Special Senses	Sudden decrease or loss of hearing					
Other Events	Nervous Seizure, seizure recurrence, anxiety, and transient global amnesia					
	Urogenital	Prolonged erection, priapism, and hematuria.				
	Special Senses	Diplopia, temporary vision loss/decreased vision, ocula redness, ocular burning, ocular swelling, increased intraocular pressure, retinal vascular disease, vitreous detachment/traction, paramacular edema, and epistax				
	Non-arteritic anterior ischemic optic neuropathy (NAION)	Decreased vision including permanent loss of vision. NAION reported rarely post-marketing in temporal association with use of Viagra mostly in patients with risk factors including: Low cup to disc ratio, age over 50, diabetes, hypertension, coronary heart disease, hyperlipidemia, and smoking.				

 Table 7. Incidence of Clinical Worsening and Most Frequent Adverse Events in Daily Dosing of

 Sildenafil and Placebo (dose listed was administered 3 times each day for 12 weeks)

Sildenafil Treatment for Chronic Traumatic Microvascular Injuries

Protocol UT-7529

Dose	Placebo		Sildenafil		
	Placebo				
Number of Subjects		20mg TID	40mg TID	80mg TID	
(percent Female)	n=70 (81%)	n=69 (71%)	n=67 (70%	n=71 (79%)	
Clinical worsening	7 (10%)	3 (4%)	2 (3%)	5 (7%)	
Death	1 (1%)	0	1 (1%)	2 (3%)	
Hospitalization for pulmonary	7 (10%)	2 (3%)	2 (3%)	2 (3%)	
arterial hypertension					
Initiation of prostacyclin	1 (1)	0	0	0	
Initiation of bosentan	0	0	1 (1)	0	
Adverse Events	Placebo	Sildenafil			
		20mg TID	40mg TID	80mg TID	
Headache	27 (39%)	32 (46%)	28 (42%)	35 (49%)	
Flushing	3 (4%)	7 (10%)	6 (9%)	11 (15%)	
Dyspepsia	5 (7%)	9 (13%)	6 (9%)	9 (13%)	
Back pain	8 (11%)	9 (13%)	9 (13%)	9 (8%)	
Diarrhea	4 (6%)	6 (9%)	8 (12%)	7 (10%)	
Limb pain	4 (6%)	5 (7%)	10 (15%)	6 (8%)	
Myalgia	3 (4%)	5 (7%)	4 (6%)	10 (14%)	
Cough	4 (6%)	5 (7%)	3 (4%)	6 (8%)	
Epistasis	1 (1%)	6 (9%)	5 (7%)	3 (4%)	
Pyrexia	2 (3%)	4 (6%)	2 (3%)	7 (10%)	
Insomnia	1 (1%)	5 (7%)	4 (6%)	3 (4%)	
Influenza	2 (3%)	4 (6%)	4 (6%)	3 (4%)	
Visual disturbance	0	0	3 (4%)	5 (7%)	
Gastritis	0	2 (3%)	2 (3%)	3 (4%)	

**FDA WARNING**: There is a potential for cardiac risk of sexual activity in patients with preexisting cardiovascular disease. Therefore, treatments for erectile dysfunction, including VIAGRA, should not be generally used in men for whom sexual activity is inadvisable because of their underlying cardiovascular status. We expect this will be rare in our study, which will not enroll subjects older than 50 years of age. Participants with hypotension, cardiac failure, or coronary artery disease with unstable angina are excluded from this study.

# 8.3 TIME PERIOD AND FREQUENCY FOR EVENT ASSESSMENT AND FOLLOW-UP

After enrollment into the study, a telephone follow-up will occur every 7 days. Telephone followup and clinic visits will give physician investigators an opportunity to interface with participants. Participants will be instructed to call 911 or go to the nearest emergency room in the event of a serious symptom. Investigators will carry a pager and will be available to the study participants for questions or conserns about side effects. Study participants will be cautioned against taking medications that may have possible adverse interactions with sildenafil. Licensed physicianinvestigators may prescribe medication for headache or other minor side effects. Otherwise, patients will be instructed to seek medical attention from their personnal physician.

## 8.4 REPORTING PROCEDURES

## 8.4.1 ADVERSE EVENT REPORTING

Adverse events will be reported in accordance with Federal requirements. All adverse events, serious and non-serious, expected and unexpected, related and unrelated will be tracked by the study coordinator and medical monitors. Serious or unexpected adverse events and other unanticipated problems will be reported orally as soon as possible and in writing within 7 days if life-threatening and within 15 days otherwise to the IRB and FDA. Expected or non-serious adverse events will be reported at the time of continuing review.

## 8.4.2 REPORTING OF PREGNANCY

Although extensive testing in animals has demonstrated no negative effects on the fetus, sildenafil has not been studied in pregnant women. Sildenafil is listed as Pregnancy Category B. Pregnancy is an exclusion criteria in this study. There is no effect of sildenafil on sperm count or motility of sperm in men. If a participant has been enrolled and tests positive preganancy at a later visit, she will be withdrawn from the study.

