The participants in **group 1** (single therapy) will consist of the active boxers/MMA fighters that experience significant sub-concussive blows or a concussion during competition. In this group, 65, professional male/female boxers/MMA fighters within the North Texas region will be screened and about 50 concussed athletes will be enrolled. The athletes that have at least 25 blows to the head and a Symptom Score > 1 on at least 3 items from the Rivermead Post-Concussion Questionnaire following their fight will be enrolled in this study. The research subjects will be treated with sildenafil (60mg), once at 2 hours after experiencing a concussion.

**Group 2** will consist of the active boxers/MMA fighters that experience significant subconcussive blows or a concussion during competition. In this group, 65, professional male/female boxers/MMA fighters within the North Texas region will be screened and about 50 concussed athletes will be enrolled. The athletes that have at least 25 blows to the head and a Symptom Score > 1 on at least 3 items from the Rivermead Post-Concussion Questionnaire following their fight will be enrolled in this study. Once enrolled, the subjects will be treated with sildenafil (60mg) once-a-day for 14 days.

**Healthy Control group:** In this study, 80, age (between 18 and 35)-matched healthy controls will be enrolled. The control subjects will participate in neuropsychological testing, blood/saliva collection, and the MR imaging procedures. Healthy controls will be tested in group 1 (n=40) and 2 (n=40) and randomized to receive either sildenafil or placebo in this group.

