## 5 STUDY ENROLLMENT AND WITHDRAWAL

## 5.1 PARTICIPANT INCLUSION CRITERIA

## FOR ATHLETES

- 1. Age 18-35
- 2. Male or female professional boxers/MMA fighters
- 3. Ability to undergo MR imaging procedures
- 4. At least one of the following:
  - a. KO/TKO scored by fight referee.
  - b. Greater than 25 blows to the head.
- Significant post-concussive symptoms (Symptom Score > 1 on at least 3 items from the Rivermead Post-Concussion Questionnaire)
   FOR CONTROLS
- 1. Age 18-35
- 2. Male of female who do not participate in contact sports
- 3. Screen negative for mTBI using Ohio State TBI ID

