## 5.2 PARTICIPANT EXCLUSION CRITERIA

- 1. Contraindication to sildenafil which includes the following:
  - a. Current use of organic nitrate vasodilators
  - b. Use of ritonavir (HIV-protease inhibitor)
  - c. Current use of erythromycin, ketoconazole, or itraconazole

STU032018-063, [name], FormA-ResearchProtocol, Mod\_6, 11-25-19 (1) NIH-FDA Clinical Trial Protocol

- d. Current use of cimetidine
- e. Current resting hypotension (BP < 90/50 mm Hg)
- f. Current severe renal insufficiency (Creatinine Clearance < 30mL/min)
- g. Current hepatic cirrhosis
- h. Current cardiac failure or coronary artery disease causing unstable angina
- i. Retinitis pigmentosa
- j. Known hypersensitivity or allergy to sildenafil of any of its components
- 2. Daily therapy with a PDE5 inhibitor within the past 2 months
- 3. Immediate hospitalization for severe concussion
- 4. History of neurological or psychiatric disorder not related to TBI
- 5. Known inclusion in another interventional clinical trial
- 6. Subjects with metal implants that would interfere with the MR imaging procedures
- 7. Sickle cell disease
- 8. History of priapism

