## 7 STUDY PROCEDURES AND SCHEDULE

## 7.1 STUDY PROCEDURES/EVALUATIONS

## 7.1.1 STUDY SPECIFIC PROCEDURES

Prior to performing any study procedures, consent will be obtained. All of the evaluations and procedures will performed for research purposes only. None of the tests will be for clinical purposes. In table 2, the study procedures are listed for the athletes that will be treated with sildenafil after competition and procedures for the controls.

Boxers (n=100); Controls (n=80)	Baseline	Day 1-3	Day 7 (phone)	Day 15 (phone)	Day 22 (phone)	Day 30
1. Inclusion/Exclusion Criteria	Х					
2. Informed Consent	Х					
3. Blood/saliva collection (side effects, tolerability, brain biomarkers)	Х	Х				х
4. Structural MRI (T1 MPRAGE, FLAIR, DTI, rsBOLD)	х	Х				Х
5. Randomization		Х				
6. Dispensing study drug (sildenafil or placebo)		Х				
7. Pill counting for compliance						Х
8. Monitoring for adverse effects		Х	Х	Х	Х	Х
9. Symptom inventory		Х	Х	Х	Х	Х
10. Neuropsychometric CDEs	Х	Х				Х

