## 10 STATISTICAL CONSIDERATIONS

#### 10.1 STATISTICAL AND ANALYTICAL PLANS

#### STATISTICAL ANALYSIS PLAN

#### Study design and randomization scheme

Once eligibility is confirmed, based upon defined inclusion and exclusion criteria, randomization will occur within 2 hours of a bout. The placebo-controlled double-blind design will diminish concern about predictability of treatment assignments. The unblinded study biostatistician will prepare a randomization schedule. Randomization will be 1:1 sildenafil:placebo, and will be in blocks of 2. Treatment allocation will be determined via a computer program that automatically generates random digits. Investigators associated with this study will not have access to the randomization schedule. The randomization program will also record the assignments to the corresponding boxers in the database and will display the assignments on the screen for action by the study coordinators.

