## 10.2 MEASURES TO MINIMIZE BIAS

## 10.2.1 ENROLLMENT/ RANDOMIZATION/ MASKING PROCEDURES

#### Recruitment Methods and Consenting Process:

At the baseline visit, the participants will be consented to participate in the study. After participating in the boxing match, the enrolled boxers will be re-screened and if the boxer has a Rivermead symptom score > 1 on at least 3 items from the Rivermead Post-Concussion Questionnaire or has greater than 25 blows to the head, the participant will be informed of their eligibility to participate in the study and the potential risks associated with this clinical trial.

A copy of the signed consent form will be provided to the participant/family, and one copy will remain in a locked storage facility. Both women and minorities will be enrolled in this study. Due to the study population, children will not be enrolled in this study. Previously, we have enrolled 125 boxers from the North Texas area to participate in both observational and interventional clinical trials. Recently we completed a Department of Defense (DOD) observational study aimed at measuring early brain biomarkers of injury in professional boxers. We identified numerous early predictors of outcome in these athletes. Our dropout rate is very low and previously the boxers were compliant with the study procedures (self-administering study medication, neuropsychological testing, MRI procedures). We expect a dropout rate of 10-20% and will enroll a total of 110-120 boxers to complete the proposed studies.

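### Section 8.4.2 excludes pregnancy and withdraws a participant on a later positive test, but the 5.2 list omits pregnancy and no visit or laboratory panel names a test

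*Combined protocol and SAP*

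**What the plan says.** Section 8.4.2 contains two rules. The first is "Pregnancy is an exclusion criteria in this study". The second says that a participant who has been enrolled and "tests positive preganancy at a later visit, she will be withdrawn from the study". The same section reports that animal testing showed no negative fetal effects, that sildenafil is Pregnancy Category B, and that it has not been studied in pregnant women.

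Women are eligible in both populations. Section 5.1 admits "Male or female professional boxers/MMA fighters" aged 18-35 and, in similar terms, controls of either sex in the same age range. Section 10.2.1 confirms: "Both women and minorities will be enrolled in this study". The controls also receive study drug. Section 4.1 says "Healthy controls will be tested in group 1 (n=40) and 2 (n=40) and randomized to receive either sildenafil or placebo in this group".

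The exclusion list in 5.2 has eight numbered items and ends with "8. History of priapism". Pregnancy is not among them.

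**The concern.** Both rules in 8.4.2 need something elsewhere in the protocol to carry them out. The exclusion needs an entry in the list that staff check, and a way to find out whether it applies. The withdrawal rule refers to a positive test at a later visit, so it needs a test at some visit. Neither is visible.

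At stake is the dosing of a woman with an unrecognised pregnancy whom the protocol means to keep out. The controls deserve particular notice: they are healthy volunteers, and half of any women among them would be expected to receive active drug under 1:1 allocation.

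**Working it through.** The plan states no figure on this point, so the main check is a comparison of texts. The arithmetic that follows only sizes the gap and the remedy.

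**1. Where a criterion or test could appear**

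| Place | Content | Pregnancy criterion or test |
|---|---|---|
| 5.1 inclusion | Age, sex, injury or control criteria | None; no negative test or contraception required |
| 5.2 exclusion | Items 1 to 8 in unbroken order, with 1a to 1j under item 1 | None |
| Table 2 (7.1.1) | 10 rows | None |
| 7.2.1 panel | 17 analytes | None |
| 7.2.2 other assays | N/A | None |
| 7.3.2 visit lists | Visits 1 to 5 | None |
| 7.3.3 early termination | Samples, neuropsychological tests, questionnaire, MRI | None |
| Section 9 safety draw | Toxicology, liver function, coagulation | None |

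The nearest entry is a general Visit 1 line about examinations and other assessments. It names no test and is not repeated at later visits.

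**2. When eligibility is checked.** Table 2 marks the eligibility criteria in the Baseline column only. Visit 1, which 4.1 places before the fight, lists both verification of the criteria and a blood draw. The post-bout re-screen in 10.2.1 covers only the Rivermead score and blows to the head. Baseline is therefore the natural point for a pregnancy test, and blood is already being taken there.

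**3. Exposure per affected woman on sildenafil** (dose and duration from 4.1 and 6.1.5)

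- Single-dose group: 1 × 60 = 60 mg.
- Daily group: 14 × 60 = 840 mg.

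A negative result required before dosing can prevent all of it in both groups.

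**4. What a day 1-3 test could still avoid in the daily group.** Assume the first dose is at 2 hours after injury (day 0, as in 6.1.5 and Visit 2), one dose a day, a draw on day d = 1 to 3, and a result t = 0 to 2 days later. The delay t is an assumption.

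- If the dose on the result day has not been taken, doses taken = d + t. The minimum is 1 + 0 = 1, leaving 14 − 1 = 13.
- If that day's dose has been taken, doses taken = d + t + 1. The maximum is 3 + 2 + 1 = 6, leaving 14 − 6 = 8.

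So 8 to 13 of the 14 doses are avoidable. A later first dose, as the dispensing row of Table 2 would suggest, would leave more. In the single-dose group, a day 1-3 test cannot undo a dose given at 2 hours. A day 30 test prevents no doses in either group.

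**5. Number of assays.** Let p be the share of women, which the documents do not give; assume 0.10 to 0.50. At baseline, take all 130 screened athletes (4.1) and 80 controls. At day 1-3, take the daily group only: 50 athletes (4.1), or 60 if 120 are enrolled in total (10.2.1), plus 40 controls.

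Assays = (130 + 80)p + (50 to 60 + 40)p

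- p = 0.10: 21 + 9 = 30, or 21 + 10 = 31.
- p = 0.50: 105 + 45 = 150, or 105 + 50 = 155.

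The range is about 30 to 155.

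**The case against.** The best defence is that 8.4.2 is part of the protocol and binds staff as it stands. Visit 1 verifies the exclusion criteria, takes a medical history and leaves room for other assessments. The withdrawal rule is conditional and promises no scheduled test; a woman could report a positive home test at the weekly contacts described in 8.3. The consent form, the manual of procedures and the MRI screening questionnaire are not shown and might contain a check. In the copy reviewed, some text between 7.2.4 and 7.3 is also not visible. All of this stands as a limit on the finding. It does not close the gap: history and self-report cannot detect a pregnancy that the woman does not know about, and every list the finding relies on is present and complete.

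Three stronger inferences are tempting, and the documents do not support them.

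- *The timing of randomisation leaves no room for a test.* Section 10.1 says "Once eligibility is confirmed, based upon defined inclusion and exclusion criteria, randomization will occur within 2 hours of a bout", which might suggest that a laboratory result could never be back in time. But the criteria are verified at the pre-fight baseline visit, outside that window.
- *Fetal harm is to be expected.* The documents give neither the share of women nor a rate of unrecognised pregnancy, so the number of exposed pregnancies cannot be estimated. The data reported in 8.4.2 are reassuring as far as they go.
- *The trial's results are compromised.* Nothing here touches allocation, endpoints, sample size or analysis.

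**Conclusion.** The inconsistency is real and should be corrected. Pregnancy is an exclusion in 8.4.2 but is not among the eight items of 5.2. No pregnancy test is named anywhere in the visible schedule or laboratory sections, while women aged 18-35 in both populations can be allocated sildenafil. A site that follows 5.2 and the schedule to the letter would not detect the condition that 8.4.2 excludes, and the withdrawal rule has no scheduled trigger.

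The potential exposure is 60 mg or 840 mg per affected woman on active drug. How many women that would be is unknown. The conclusion rests on the visible text. The 8-to-13-dose range rests further on a first dose at 2 hours and a result delay of 0 to 2 days.

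**What to change.** - **5.2:** add pregnancy as an exclusion for athletes and controls.
- **Table 2, 7.2.1 and Visit 1 in 7.3.2:** add a pregnancy test for women of childbearing potential, run on the baseline blood. Section 7.2.1 times its panel at day 1-3 and day 30, so the new entry must name baseline explicitly.
- **Dosing:** require a negative result before the first dose, for athletes and controls alike.
- **14-day group:** a further test on the existing day 1-3 draw is a reasonable addition. A positive result would stop dosing and trigger the 8.4.2 withdrawal while most doses remain.
- **Optional:** a maximum interval from test to first dose, a urine test as back-up, and a day 30 test.

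The cost is a few lines of text and one or two inexpensive assays per woman, with no extra blood draw. Chemistry samples go by courier to an outside laboratory (7.2.4), so the baseline result has to be back before the bout; the optional urine test would cover cases where it is not.

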## 8.5 STUDY HALTING RULES

Administration of study agent will be halted when three grade 3 AEs determined to be "probably related" are reported to the study coordinators and /or study PIs. The PIs will notify the IRB and FDA immediately when the third grade 3 event is reported and enrollment screens will stop accepting new study participants. The PI will inform the DSMP members within 24 hours of this occurrence and will provide the DSMP group with AE listing reports. The DSMP members will convene an ad hoc meeting by teleconference or in writing as soon as possible. The DSMP members will provide recommendations for proceeding with the study to the study sponsor. The PI will inform the FDA of the temporary halt and the disposition of the study.

